Assessment of Post-surgical improvement in Obstructive Sleep Apnea Patients after imaging of Upper Respiratory Airway using Cone Beam Computed Tomography (CBCT) and Drug-Induced Sleep Endoscopy (DISE) versus Drug-Induced Sleep Endoscopy Only: A Validity Study

Registered at www.clinicaltrials.gov. ID: OCS05051989

Protocol submitted to
Faculty of Dentistry, Cairo University
for partial fulfilment of the requirements for the Ph.D. Degree in Oral and Maxillofacial Radiology,
Faculty of Dentistry, Cairo University

By

[name]

**Teaching Assistant of Oral Medicine, Periodontology, Diagnosis and Oral Radiology Department,
Faculty of Oral and Dental Medicine,
Delta University for Science and Technology**

BDS 2011, MSc, MFDS RCSD

Date: 22/01/2021

Code: RAD 7-1-1

Supervisors' signature

1- [name] [name]
Associate Professor of Oral and Maxillofacial
Radiology Department,
Faculty of Dentistry, Cairo University

Head of the department's
signature

[name]
Head of Department and Professor of
Oral and Maxillofacial Radiology
Department, Faculty of Dentistry, Cairo
University

2- [name] [name]

Lecturer of Oral and Maxillofacial Radiology
Department, Faculty of Dentistry, Cairo
University

**3- [name] [name]**

Associate Professor of ENT Department, Faculty
of Medicine, Mansoura University

I- Study Protocol:

A) Study design and setting

1. Study design

In this validity two-arm study, a total of (70) patients will be included; all are diagnosed with OSA and will undergo surgical treatment after appropriate planning. Patients will be classified into two equal groups (with allocation ratio 1:1). Patients of the study group will be examined after scanning with CBCT at both ends of expiration and inspiration and DISE. Control group patients will be examined by DISE only.

These (70) patients will be selected by the ENT specialist according to the following;

- A multidisciplinary approach will be performed to diagnose OSA patients who are indicated for surgery. Firstly, a comprehensive assessment of patients' history will be performed; including evaluation of all risk factors and complete sleep history (*Epstein et al. 2009*).
- Epworth Sleepiness Scale (ESS) which consists of eight section questionnaire that defines the frequency of an individual to fall asleep during regular daily activities will be obtained from the patients (*Johns 1992, Sharkey et al. 2013*).
- Afterward, a proper physical examination will be performed including a thorough clinical examination of the oropharynx, nasopharynx, and hypopharynx to evaluate any anatomical abnormalities as impotency of the nasal airway, elongated soft palate or uvula, enlarged lingual tonsils, and any other pathological conditions of tongue, palate, and tonsils.
- Then, Polysomnography (PSG) (sleep study) will be performed to allow proper evaluation of normal and abnormal physiological sleep episodes. Apnea/Hypopnea Index (AHI) will be reported to detect the severity of OSA and patients were classified into mild (AHI = 5-14 / hour), moderate (AHI = 15-30 / hour) and severe (AHI >30 / hour) (*Maspero et al. 2015*).
- All patients in both groups will undergo upper airway surgery, DISE will be performed by the same ENT surgeon to detect the level of collapse in the upper airway which will be assessed by LwPTL and VOTE classifications, emphasizing on the primary structures contributing at upper airway collapse, either alone or in combination: the larynx, palate, tongue and pharyngeal lateral walls.
- Study group participants only will be scanned by CBCT twice; once at the end of inspiration and the other at the end of expiration while they are gently holding their breath for as long as possible. (*Woodson 2003*)
- In the study group, surgical procedures decision will be taken after appropriate assessment to sites of collapse in CBCT views at both ends of expiration and inspiration vies in combination to DISE.
- Finally, strict post-operative instructions will be given to patients of both groups.

2. Settings

This study will be carried out on patients attending outpatient clinics in the ENT department, Faculty of Medicine, Mansoura University, Egypt. CBCT scans of surgical candidates of OSA patients will be included

according to the proposed eligibility criteria.

B) Participants

1. Eligibility criteria and selection methods

Inclusion Criteria:

- Patients' age is more than 18 years old.
- Patients are indicated for upper respiratory airway surgery based on adequate history taking, proper clinical examination, and sleep study.
- Patients refusing non-surgical treatment procedures as Continuous Positive Airway Pressure (CPAP) treatment.
- Systemically medically free patients.

Exclusion Criteria:

- Patients who are refusing the surgical approach as a treatment option.
- Patients who have undergone previous surgeries in the upper respiratory airway.
- Pregnant women.
- Patients who didn't follow post-operative instructions.
- Patients who are not able to come for the follow-up appointments.

Follow up:

- Patients who strictly follow post-operative instructions will perform another sleep study after 3 months from the day of the surgery.
- Percentage of AHI reduction will be calculated which in turn indicates post-surgical improvement.

2. Matching criteria and allocation ratio

The patients will be randomly allocated to the intervention groups using computer-generated random numbers that will be performed by the main investigator ([name]). The patients will be allocated in a ratio of 1:1 (35 patients in each group).

The two groups will be equally clinically examined before surgical procedures. Then the decision of which group will be scanned with CBCT and which won't will be taken according to the randomized numbers placed in opaque sealed envelopes. The number will be picked by the main investigator ([name]).

The main investigator will be responsible for the generation of allocation sequence and will assign the patients to the 2 intervention groups. The main investigator will also be responsible for patient enrolment.

C) Variables

1. Details about variables

- Mean AHI reduction percentage.
- Level of Collapse of the upper respiratory airway.
- The volume of the upper respiratory airway.

2. Data sources and management

- The level of the collapse of the upper respiratory airway will be determined by an expert ENT surgeon with DISE.
- Radiographic assessment will be performed using the iCAT FLX V17-Series CBCT machine (Imaging Science International, ISI, PA, USA). Quick scan imaging protocol of 16cm x 13cm Field Of View (FOV) (120 KV, 5 mA, 2 sec) and 0.3 mm voxel size.
- Participants are required to wear a protective lead apron during scanning. The position of the X-ray tube will be adjusted to minimize the extent of scanning and to ensure the lowest radiation dose as much as possible. To prevent motion artifacts, participants will be instructed not to move their head, body, tongue, and jaws during scanning.
- Raw DICOM data from CBCT scanning will be checked to evaluate whether there were any motion artifacts in images at coronal, horizontal, and sagittal planes.
- CBCT scans at both ends of inspiration and expiration will be analyzed using Invivo5 software.
- For the second outcome, CBCT images will be interpreted by three oral and maxillofacial radiologists independently; blinded from demographic data of the patients, DISE findings, and the results of each other.
- Each radiologist will evaluate the CBCT images for assessment of the level of collapse and assessment of the secondary outcomes. One radiologist will assess all the outcomes twice with more than 1month interval. Intra-observer and inter-observer variability of CBCT findings will be evaluated.

3. Addressing potential sources of bias

No source of bias. CBCT images will be interpreted by three oral and maxillofacial radiologists independently blinded from demographic data of the patients, DISE findings, and the results of each other.

D) Study size

1. Study size

This study aims to assess surgical improvement in OSA patients after imaging of upper Respiratory Airway using CBCT and DISE using mean AHI reduction percentage. According to the results of (**Pang et al. 2020**), the mean of AHI reduction percentage and the minimal clinically important difference estimated by the expert was 21.6. By adopting an alpha (α) level of 0.05 (5%) and a power of 80%, the predicted sample size is 35 per group with a total of 70. To compensate for losses during follow up, the sample will be

increased by 20% to be 84 participants in total. Sample size calculation was achieved using PS: Power and Sample Size Calculation software Version 3.1.2 (Vanderbilt University, Nashville, Tennessee, USA).

E) Quantitative variables

1. Handling of quantitative variables in the analyses

The volume of the upper respiratory airway will be determined and correlated with its level of collapse.

F) Statistical methods

1. Statistical methods

Data will be analyzed using SPSS (statistical package for social sciences) version 22. Qualitative data will be presented as number and percent, Quantitative data will be tested for normality by the Kolmogorov-Smirnov test then described as mean and standard deviation for normally distributed data and median and range for non-normally distributed. The appropriate statistical test will be applied according to the data type with the following suggested tests: Chi-Square for the categorical variable. Student t-test and Mann Whitney U test for continuous variables.

II. Ethics and dissemination:

a. Research ethics approval

The study protocol will be submitted to the Ethics committee in the Faculty of Dentistry, Cairo University for approval.

b. Protocol amendments

Any amendments in the protocol will be reported to the main and co-supervisors.

c. Informed consent

After discussing the treatment plan with the patient and educating the patient with all the data needed, an arabic consent form will be signed by the willing participants.

d. Confidentiality

- All study-related information will be stored securely.
- All reports, data, scans, and administrative forms will be identified by a coded ID (identification) number only to maintain participant confidentiality.
- All personal data that contain names or other identifiers including age, sex, identification number, address, phone number, work address, and any other information will be stored separately from the study records and identified by a code number.

e. Declaration of interest

There is no conflict of interest.

f. Access to data

Investigator, Co-supervisors, and main supervisor will have access to the final trial data set .

g. Dissemination policy

The Investigator will communicate his results with other participants and healthcare providers through the publication of the protocol and the research final results and recommendations. This will be done through publication websites and journals concerned with Oral and Maxillofacial Radiology specialty, For Sharing the recommended clinical application obtained from the final results of the research.

III- Appendix:

1- Epworth Sleepiness Scale (ESS):

Epworth Sleepiness Scale

Name: _____ Today's date: _____

Your age (Yrs): _____ Your sex (Male = M, Female = F): _____

How likely are you to doze off or fall asleep in the following situations, in contrast to feeling just tired?

This refers to your usual way of life in recent times.

Even if you haven't done some of these things recently try to work out how they would have affected you.

Use the following scale to choose the **most appropriate number** for each situation:

- 0 = would never doze
- 1 = slight chance of dozing
- 2 = moderate chance of dozing
- 3 = high chance of dozing

It is important that you answer each question as best you can.

Situation	Chance of Dozing (0-3)
Sitting and reading	_____
Watching TV	_____
Sitting, inactive in a public place (e.g. a theatre or a meeting)	_____
As a passenger in a car for an hour without a break	_____
Lying down to rest in the afternoon when circumstances permit	_____
Sitting and talking to someone	_____
Sitting quietly after a lunch without alcohol	_____
In a car, while stopped for a few minutes in the traffic	_____

THANK YOU FOR YOUR COOPERATION

© M.W. Johns 1990-97

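### AHI reduction is compared only in patients who adhered after surgery, a subset selected after randomisation

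*Combined protocol and SAP*

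**What the plan says.** All references are to the combined protocol and SAP, part I.

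- **Allocation (B.2, Matching criteria and allocation ratio).** After the clinical examination, sealed envelopes settle who is scanned: "Then the decision of which group will be scanned with CBCT and which won't will be taken according to the randomized numbers".
- **Use of the scan (A.1, Study design).** "In the study group, surgical procedures decision will be taken after appropriate assessment to sites of collapse in CBCT views", together with DISE. Allocation therefore comes before surgery. Post-operative instructions are given to both groups as the last step.
- **Exclusion criteria (B.1).** The list includes "Patients who didn't follow post-operative instructions" and "Patients who are not able to come for the follow-up appointments".
- **Follow up (B.1).** "Patients who strictly follow post-operative instructions will perform another sleep study after 3 months from the day of the surgery". Then: "Percentage of AHI reduction will be calculated which in turn indicates post-surgical improvement".
- **Outcome (C.1 and D.1).** Mean AHI reduction percentage is the first variable listed and the one used for the sample size. The protocol does not label a primary outcome, so I infer that this is it.
- **Losses (D.1).** "To compensate for losses during follow up, the sample will be" raised by 20%, to 84.
- **Bias (C.3).** "No source of bias". The only support offered is the blinding of the radiologists who read the CBCT images.
- **Analysis (F.1).** The t-test and Mann-Whitney test are named. No analysis set and no rule for missing AHI are given.

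**The concern.** Whether a patient followed post-operative instructions can be known only after surgery, and so only after allocation. Using it as an exclusion removes randomised patients for something that allocation may have influenced. In the study arm CBCT contributes to the choice of operation, so the procedure, the recovery and the ability or willingness to comply could all differ from the control arm. The judgement itself is also open: strict adherence is not defined, no assessor is named, and no blinding of that judgement is described. The main investigator generates the sequence, enrols and assigns.

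Randomisation makes the two full arms comparable. It does not make the adherent parts of the two arms comparable.

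The rule also governs data collection as well as analysis. Non-adherers have no planned 3-month AHI, so nobody can later check from observed data whether leaving them out mattered.

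**Working it through.** **1. Order of events.** Examination → envelope → CBCT or no CBCT → surgical decision → surgery → post-operative instructions → adherence judged → sleep study at 3 months, strict adherers only. The exclusion falls after allocation, and no other section schedules a sleep study for the patients it removes. The attendance criterion could be a screening judgement; its timing is not stated, so nothing here rests on it.

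**2. The plan's own figures.** Section D.1 gives 35 per group, α 0.05, power 80% and a difference of 21.6, which I read as percentage points of AHI reduction. It gives no SD, so 35 cannot be reproduced, only solved backwards. Two-sided normal approximation: SD = 21.6 / [√(2/35) × (1.960 + 0.842)] = 32.3. Exact noncentral t: SD = 31.8, which is used below. The total of 84 is 70 × 1.20.

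**3. Simple bias model (assumed inputs).** Suppose there is no true difference among all randomised patients, and non-adherers improve by *g* points less than adherers in both arms. If a proportion *p* of an arm is excluded, the mean of those kept exceeds the mean of the full arm by *p·g*. The spurious difference is therefore

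bias = (p₂ − p₁) × g

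With 42 per arm, SE = 31.8 × √[1/(42(1−p₁)) + 1/(42(1−p₂))]. The false-positive rate is the two-sided normal rejection probability at bias/SE.

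| Excluded (p₁ vs p₂) | g | Bias (points) | SE | False-positive rate |
|---|---|---|---|---|
| 20% vs 20% | any | 0 | 7.8 | 5.0% |
| 10% vs 20% | 10 | 1.0 | 7.5 | 5.2% |
| 10% vs 20% | 30 | 3.0 | 7.5 | 6.8% |
| 10% vs 30% | 10 | 2.0 | 7.8 | 5.8% |
| 10% vs 30% | 30 | 6.0 | 7.8 | 12.0% |

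A bias of 6.0 points is 6.0/21.6 = 28% of the target difference.

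**4. Equal numbers excluded, different kinds of patient.** Equal exclusion rates are not enough. Let the probability of being kept be logistic(a + b·z), where z is standardised improvement and a is set to give the stated retention. Then bias = 31.8 × (E[z | kept, one arm] − E[z | kept, other arm]). A slope b = 1 at 80% retention keeps 66%, 84% and 93% of patients at −1, 0 and +1 SD of improvement. At 80% retention E[z | kept] is 0 for b = 0, 0.096 for b = 0.5 and 0.173 for b = 1. SE = 31.8 × √(2/33.6) = 7.8.

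- Same slope and same retention in both arms: bias 0, false-positive rate 5%.
- Slopes 0.5 vs 1: 31.8 × (0.173 − 0.096) ≈ 2.4 points, 6%.
- Slopes 0 vs 1: 31.8 × 0.173 = 5.5 points, 11%.
- Slopes 0 vs 1 with 10% lost: 2.9 points, 7%. With 30% lost: 8.0 points, 16%.
- Same slope in both arms but 90% vs 70% retained: 3.0 points, 7% (b = 0.5); 5.2 points, 10% (b = 1).
- Opposite slopes, −1 vs +1: 11.0 points, 29%. This is an outer bound; the documents suggest no mechanism for it.

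**The case against.** The strongest reply is that differential selection is possible but not shown. Both arms receive the same post-operative instructions, all patients have upper airway surgery, and the same surgeon performs DISE. The documents give no adherence rate, overall or by arm, and the chain from CBCT to a different operation to different adherence is an inference. This stands: the bias is a risk, and it is zero if exclusions are alike.

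The illustration is open to criticism too. The rule selects on adherence, while the logistic model selects on improvement itself, and no section links the two. The 20% is the allowance for losses, not a stated rate of non-adherence. Intermediate scenarios move the false-positive rate only to 6% or 7%. These points stand as limits on the figures.

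Three defences do not succeed:

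- **The 20% increase covers it.** The increase replaces numbers. It does not address which patients are lost.
- **This is simply a per-protocol analysis.** The effect in adherers is a legitimate question if declared, but the protocol does not declare it, and its data-collection rule leaves no all-randomised alternative to report beside it.
- **One rule applied equally to both arms is safe.** That holds in the model when there is no true effect. With a true effect of 21.6 points and one common retention rule (80% kept overall), the observed difference becomes about 20.8 (slope 0.5) or 19.2 (slope 1), because the better arm keeps more of its patients.

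**Conclusion.** The concern holds, and it should be fixed before patients reach the 3-month visit. It rests on a stated rule, not on a missing detail: followed as written, the plan compares AHI reduction in a subset formed after randomisation and collects nothing from the rest.

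Neither the size nor the direction of any bias can be known from the documents. Under the assumptions shown (no true effect, back-solved SD 31.8, 84 enrolled, 10% to 30% excluded), it runs from zero to about 8 points against a target of 21.6, with false-positive rates from 5% to about 16%. Only opposite selection in the two arms goes beyond that. The plausible cases are mostly modest. The seriousness comes from losing the randomised comparison and from having no data with which to test the consequence afterwards.

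**What to change.** Core changes:

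1. Remove non-adherence to post-operative instructions from the exclusion criteria in B.1.
2. Schedule the 3-month sleep study for every randomised patient, whatever their adherence. For a randomised patient who is not operated on, state the reference date; the scheduled surgery date would serve.
3. State in F.1 that patients are analysed in the arm to which they were allocated, and report losses by arm with reasons.
4. Reword the attendance criterion as a judgement made at screening, before the envelope is opened.
5. Name one method in advance for any AHI still missing. Some non-adherers will not attend, so scheduling alone will not complete the data.

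Supporting changes, where the detail is a matter of choice: add a sensitivity analysis in which missingness depends on outcome, for example shifting the missing patients' AHI reduction by 10, 20 and 30 points in one arm at a time and reporting where the conclusion changes. Keep the strict-adherer comparison as a labelled supplementary analysis, with adherence defined. Replace the statement in C.3 that bias is absent.

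The cost is protocol wording plus sleep studies for non-adherers and any unoperated patients, all already within the planned number. At an assumed 20% non-adherence of 84, that is at most 0.20 × 84 = 16.8, about 17 extra studies. The estimated effect may be somewhat smaller than among strict adherers. No rule of surgical or post-operative care needs to change.

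### The allocation section randomises 35 per group (70), but the study-size section raises the sample to 84 (42 per group) to cover losses, so the loss allowance never reaches the allocation

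*Combined protocol and SAP*

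**What the plan says.** - **I.D.1 Study size.** At 5% alpha and 80% power, "the predicted sample size is 35 per group with a total of 70". The section continues: "To compensate for losses during follow up, the sample will be" "increased by 20% to be 84 participants in total". (The sentence crosses a page break, but no words are lost.)
- **I.B.2 Matching criteria and allocation ratio.** "The patients will be allocated in a ratio of 1:1 (35 patients in each group". Who is scanned with CBCT "will be taken according to the randomized numbers placed in opaque sealed envelopes".
- **I.A.1 Study design.** It refers twice to 70 patients, once as included and once as selected. For the study group, "surgical procedures decision will be taken after appropriate assessment to sites of collapse in CBCT views", in combination with DISE.
- **I.B.1 Eligibility criteria, exclusions and follow-up.** "Patients who didn't follow post-operative instructions" are excluded, as are patients unable to attend follow-up. "Patients who strictly follow post-operative instructions will perform another sleep study after 3 months from the day of the surgery".

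The figure 84 appears only in I.D.1. The figure 42 per group appears nowhere. No section describes 35 or 70 as completers or evaluable patients.

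**The concern.** I.D.1 treats 70 as the size needed for the analysis and 84 as the size needed to allow for attrition. I.B.2, which governs the random sequence and the envelopes, uses the figure without the allowance. A team that works from I.B.2 will stop at 70 and have no reserve.

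The protocol itself expects losses. The outcome, percentage AHI reduction, needs a sleep study 3 months after surgery, and patients who do not follow post-operative instructions are removed. Every such loss then takes the comparison below the size on which the 80% power rests.

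Approval is also affected. The protocol is still to be submitted to the ethics committee, which cannot tell from the text whether it is being asked to approve 70 or 84 patients, that is, 35 or 42 people scanned twice by CBCT.

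**Working it through.** **1. Reproduce the plan's figure.** Inputs from I.D.1: 35 per group, 70 in total, 20% increase.
- 70 × 1.20 = 84, as stated.
- 84 / 2 = 42 per group at the 1:1 ratio of I.B.2.
- Gap against I.B.2: 84 − 70 = 14 patients, 7 per group.

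**2. Establish when the 35 per group are counted.** The order of events in the protocol is:
1. Envelope allocation decides who has CBCT (I.B.2).
2. The study group's surgical decision follows assessment of the CBCT views (I.A.1).
3. Surgery takes place.
4. Patients who do not follow post-operative instructions are removed (I.B.1).
5. The remaining patients have the 3-month sleep study (I.B.1).

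I.B.2 counts patients at step 1, and the losses occur at steps 4 and 5. An allowance for those losses must therefore be included in the step 1 number. The mentions of 70 in I.A.1 agree with I.B.2 but are weaker evidence, because the list there runs on through surgery and *included* could be read as evaluable.

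**3. Set up the power calculation.** The SD behind the 35 per group is not stated, so the standardised effect d is worked back from the stated size. With n per arm:
- noncentrality = d × √(n/2), degrees of freedom = 2n − 2, two-sided 5% t test;
- the unrounded size lies between 34 and 35, so d is set to give exactly 80% at n = 35 (low end, d = 0.679) or at n = 34 (high end, d = 0.690).

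By construction, power at 35 per arm is then 80.0 to 81.2%.

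**4. Results, with losses balanced between arms** (fractional n where the percentage does not give whole patients):

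| Randomised | Loss | Evaluable | n per arm | Power |
|---|---|---|---|---|
| 70 | 5% | 66.5 | 33.25 | 77.9 to 79.1% |
| 70 | 10% | 70 × 0.90 = 63 | 31.5 | 75.6 to 76.8% |
| 70 | 20% | 70 × 0.80 = 56 | 28 | 70.4 to 71.7% |
| 84 | 10% | 75.6 | 37.8 | 83.0 to 84.1% |
| 84 | 16.7% (14 lost) | 70 | 35 | 80.0 to 81.2% |
| 84 | 20% | 84 × 0.80 = 67.2 | 33.6 | 78.3 to 79.5% |

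**5. How many losses can 70 absorb?** At the high end (d = 0.690), 35/34 gives 80.6%, 34/34 gives 80.0% and 34/33 gives 79.4%. So at most two losses in total (2/70 = 2.9%), one per group, keep 80%. At the low end (d = 0.679) a single loss already gives 79.4%.

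**6. Sensitivity to sidedness.** If the 5% is one-sided (d = 0.600 to 0.609), 70 randomised gives 78.2 to 79.2%, 76.2 to 77.2% and 71.7 to 72.8% at 5%, 10% and 20% loss. The picture does not change.

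**7. What 84 covers.** 1 − 70/84 = 16.7%. The stated increase therefore protects 70 evaluable patients against losses of up to 14 of 84, not against a full 20%.

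**The case against.** The strongest counter-argument is that 35 per group in I.B.2 means evaluable patients. Non-compliance with post-operative instructions and inability to attend follow-up are listed as exclusion criteria, so on the protocol's own rules a patient lost in this way is not an eligible participant, and the 35 could be those left afterwards. This does not rescue the text. The sentence in I.B.2 is about allocation, allocation precedes surgery, and no section labels 35 or 70 as completers. I.B.2 does not state the length of the sequence, but the only allocated number it gives is 35 per group.

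It can also be said that I.D.1, the dedicated section, does handle losses, so this is probably a number that was not carried across, and harm follows only if the team works from I.B.2. That is fair as an account of the cause. It does not settle which number governs, and I.B.2 is where someone preparing the envelopes would look.

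Two limits stand. The mismatch does not bias any estimate; it costs power and clarity. The power figures are conditional: the effect size is worked back from the sample size, the 5% and 10% loss rates are illustrative, and the Mann-Whitney alternative in section I.F.1 is not modelled. The contradiction itself depends on none of these assumptions.

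**Conclusion.** The concern holds and must be fixed. The number to randomise is given as 70 in I.B.2 and as 84 in I.D.1, a difference of 14 patients, and reading 35 per group as evaluable patients does not reconcile them.

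Following I.B.2 discards the protocol's own allowance and leaves 80% power only with almost no loss. The cost is roughly 2 percentage points of power at 5% loss, 4 at 10% and 10 at 20%, under the assumptions given in the working. The direction is certain; the exact figures cannot be confirmed until the SD, sidedness and expected loss rate are stated.

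**What to change.** Before the allocation sequence is generated:

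- **I.B.2:** replace 35 with *42 patients in each group*.
- **I.A.1:** change both mentions of 70 to 84.
- **I.D.1:** label the calculated size as *35 evaluable patients per group with a total of 70*, and add: *84 randomised keeps 70 evaluable for losses up to 16.7% (14 of 84); at 20% loss about 67 remain.*

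The back-calculated power figures above should not be written into the protocol, since they rest on an assumed effect size.

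If the sponsor intends to randomise only 70, I.D.1 should instead drop the 84 and say that 80% power holds only without appreciable loss.

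**Cost.** Measured against I.D.1, which already commits to 84, the first option is a wording change. Measured against I.A.1 and I.B.2, it means 14 more patients, 7 of them scanned twice by CBCT. Keeping 70 adds no patients but weakens the power claim.

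### One person generates the allocation list, draws the number, assigns the arm and enrols patients, so allocation concealment is not assured and the claim of no bias is unsupported

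*Combined protocol and SAP*

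**What the plan says.** All references are to the combined protocol and SAP.

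- **Section B.2 (Matching criteria and allocation ratio)** has the main investigator produce the computer-generated random numbers and adds: "The main investigator will be responsible for the generation of allocation sequence and will assign the patients to the 2 intervention groups". It also says "The number will be picked by the main investigator" and "The main investigator will also be responsible for patient enrolment". The numbers go into opaque sealed envelopes, and the ratio is 1:1 with 35 patients per group. Before the envelope step, "The two groups will be equally clinically examined before surgical procedures".
- **Section A.1 (Study design)** says that the "patients will be selected by the ENT specialist according to the following", and then lists history, sleepiness scale, examination and sleep study. It also says "Study group participants only will be scanned by CBCT twice", and that CBCT informs the surgical decision in that group.
- **Section C.3 (Addressing potential sources of bias)** opens with "No source of bias". The one measure it then cites is independent reading of the CBCT images by three radiologists, blinded to demographics, DISE findings and each other's results.
- **Section II.c (Informed consent)** places consent after discussion of the treatment plan and does not mention allocation.

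The plan does not say whether the envelopes are numbered or opened in order, who prepares and keeps them, or whether consent precedes the envelope.

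**The concern.** Concealment means that whoever decides on a patient's entry cannot know which arm comes next. Here the person who enrols is also the author of the list and draws the number, so the separation that sealed envelopes are meant to provide is missing.

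The comparison of AHI reduction, which is the basis of the sample size in section D.1, depends on randomisation for comparable arms. If the enroller can know the next arm, that knowledge can influence who enters and when. Analysis cannot reliably remove the resulting imbalance. The tests named in section F.1 (chi-square, t-test, Mann-Whitney) include no covariate adjustment.

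The surgeon necessarily knows the arm, because CBCT feeds into the surgical decision in one group only. Protection before allocation therefore matters more. A section that declares the design free of bias tells readers that none of this needs attention.

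**Working it through.** **Step 1. Does any stated safeguard conceal the list from its author?**

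| Safeguard | Section | What it does | What it leaves open |
|---|---|---|---|
| Opaque sealed envelopes | B.2 | Hide the next arm from others | The author of the list also draws and enrols; no numbering or independent custody is stated |
| ENT specialist selects candidates | A.1 | Limits the enroller's discretion | Enrolment stays with the main investigator; nothing bars deferring or declining a patient |
| Examination before the envelope | B.2 | Puts the clinical assessment first | Does not say that consent and eligibility are recorded by then |
| Blinded CBCT reading | C.3 | Sound for collapse level and observer agreement | Scans exist in one arm only; does not touch allocation or the AHI outcome |

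None of the four closes the gap.

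**Step 2. How predictable is the next arm?** The plan gives no figure of its own to reproduce.

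*Envelopes used in list order.* The author of the list can know every next arm.

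*Envelopes shuffled.* Assume a fixed n:n pool, as the 35 per group in section B.2 suggests. Someone who keeps the tally and always guesses the under-filled arm has an expected number of correct guesses of

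n + 0.5 × (4ⁿ / C(2n, n) − 1).

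- n = 35 (the 70 in section B.2): 39.76 of 70 = 56.8%, against 35 of 70 by chance. A simulation of 20,000 lists gave 39.77.
- n = 42 (half of the 84 in section D.1): 47.26 of 84 = 56.3%.

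Under simple randomisation without a fixed pool, the tally would give 50%.

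**Step 3. What would the remedy leave behind?**

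- *Single permutation in independent custody.* The known-list case disappears and the 56–57% tally guess remains. Once one arm is full, the remaining slots are certain: on average 2n/(n+1), which is 70/36 = 1.94 for n = 35 and 84/43 = 1.95 for n = 42.
- *Undisclosed random blocks instead.* With 70 patients, the same guessing rule and 20,000 lists each, sizes 4/6 gave 48.4 correct (69.1%), 2/4/6 gave 49.1 (70.1%) and 4/6/8 gave 47.5 (67.8%). Small blocks are more predictable to anyone who keeps the tally.
- *An 84-slot list (42:42) stopped at 70.* The count in one arm is hypergeometric(84, 42, 70), and the SD of the difference between arms is 3.44 patients. The chance of a split no worse than 38:32 is 0.962. At 38:32 the effective size is 4 × 38 × 32 / 70 = 69.49 of 70, a loss of 0.7%. In the remaining 4% or so of cases the loss is larger.

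**Step 4. Size of the bias.** This cannot be derived from the documents. Purely as illustration, assume that foreknowledge shifts the arms apart by b standard deviations, with 35 per group. The test statistic is then displaced by b / √(2/35), and the two-sided 5% error rate becomes about 7% for b = 0.1, 13% for b = 0.2 and 24% for b = 0.3. The shifts are assumed, and the conclusion does not rest on them.

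**The case against.** The strongest reply is that the harm depends on a detail the plan leaves out. If the number is drawn at random from shuffled envelopes, its author does not know the next arm. Predictability is then already the 56–57% that would remain after the fix. That figure therefore describes what remains under an assumed fixed pool and does not measure the defect. This is correct. But the plan does not state that envelopes are shuffled, and where the same person makes the list, draws from an unnumbered set and enrols, nothing allows the draw to be verified.

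A second reply is that the ENT specialist largely decides candidacy, which leaves the list-holder little discretion. This carries some weight. It is still partial, because section B.2 expressly keeps enrolment with the main investigator.

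Third, the plan proposes no blocks, so the block figures rebut nothing in it. That is so; they serve only to specify the remedy.

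Fourth, other threats to the same comparison, such as the absence of any stated blinding of the 3-month sleep-study scoring, would remain after the bias section is rewritten. They are separate matters and do not weaken this one.

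Finally, a supervisor who holds the envelopes might also be a CBCT reader, whose blinding could suffer. The documents do not say who the readers are. The holder needs only a coded ID, so this is manageable.

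**Conclusion.** The concern holds and should be corrected before enrolment, because concealment cannot be restored afterwards. The text gives one person all four roles, and no stated safeguard conceals the list from that person. The right strength is that concealment is not assured; nothing in the documents shows that it will be broken.

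The statement that there is no source of bias has no support for the between-arm comparison. The magnitude is bounded only in terms of predictability: up to complete foreknowledge if list order is followed, and the tally guess if envelopes are shuffled from a fixed 1:1 pool. The judgement rests on the missing separation of roles and on the reliance of the AHI comparison on randomisation, not on any computed amount of bias.

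**What to change.** 1. **Separate the roles.** An existing team member who neither enrols nor treats patients generates the list as one 1:1 permutation without small blocks. It should cover the whole number to be enrolled (42:42 if the 84 in section D.1 are enrolled). That person prepares and keeps sequentially numbered, opaque, sealed envelopes. Each is opened in order, only once consent, eligibility and the already planned baseline examination have been recorded. The holder should receive a coded ID only.
2. **Rewrite section C.3.** Replace the claim of no bias with a description of these safeguards, and state that the surgeon cannot be blinded to arm. Keep the blinded CBCT reading, described as protection for the collapse-level and observer-agreement aims.

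**Cost.** Protocol wording and one reassigned task, with no added visit or procedure. No extra staff is needed, provided that a suitable team member is available. Each patient needs one contact with the envelope holder. This may be by telephone, because the supervising radiologists are at Cairo University and recruitment is at Mansoura University (section A.2). Without blocks, the arms may end slightly unequal if enrolment stops early, and about the last two slots of the list are certain to anyone who keeps the tally.
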